1. OBJECTIVES

Cutaneous lupus erythematosus (CLE) produces distressing symptoms including itch, pain, and disfigurement. Therapeutic options are limited and involve a significant degree of risk due to their side effect profile. To address this deficiency, we propose an open-label study to determine the efficacy of low dose UVA1 phototherapy in treating cutaneous lupus patients. This will be complemented by safety, quality of life, and immunological studies to assess the value of treating cutaneous lupus patients with low dose UVA1 phototherapy.

Primary Aim: To determine the effect of low dose UVA1 phototherapy on CLE lesions.

- Hypothesis: CLE patients treated with low dose UVA1 phototherapy will experience clinical improvement.

Secondary Aims

Aim 1: To determine the safety of low dose UVA1 phototherapy in CLE patients.

- Hypothesis: UVA1 phototherapy will have minimal side effects in CLE patients.

Aim 2: To assess effect of low dose UVA1 phototherapy on the quality of life of CLE patients

- Hypothesis: UVA1 radiation will have minimal side effects.

Aim 3: To assess immunologic effect of low dose UVA1 phototherapy in CLE patients

- Hypothesis: UVA1 radiation will decrease levels of circulating autoantibodies and T_H1 cells, and decrease T cells, B cells, and plasmacytoid dendritic cells in skin.

2. BACKGROUND

Approximately 70% of SLE patients have cutaneous manifestations including malar erythema.¹ Cutaneous lupus erythematosus has been classified into three major subtypes: acute cutaneous lupus (ACLE), which is defined as patients with SLE who fulfill at least four out of the 11 criteria outlined by the American College of Rheumatology,² and cutaneous lesions, subacute cutaneous lupus erythematosus (SCLE), which is manifested by psoriasiform or annular lesions in photosensitive areas, and chronic cutaneous lupus erythematosus, with discoid lupus (DLE) being the most common subtypes.³

Ultraviolet light therapy (phototherapy) is an established, first line therapy for several immunologically mediated disorders, including psoriasis, cutaneous T-cell lymphoma, and vitiligo. Two main types of phototherapy are currently available: UVB (290-320 nm) and UVA (320-400 nm). The UVB spectrum produces sunburn erythema and is the predominant source of photosensitivity in lupus erythematosus. UVA produces far less erythema and because of its longer wavelength, penetrates to the deep dermis where it can interact with antigen presenting cells (APCs) and T cells, potentially exerting systemic effects. UVA is subdivided into UVA1 (340-400 nm) and UVA2 (320-340 nm). UVA1 generally does not provoke photosensitive diseases.⁴

The mechanism of action of UVA1 in human SLE is unclear, but initial trials of low dose UVA1 in SLE patients demonstrated a significant decrease in the frequency of peripheral blood interferon γ -producing T_H1 and T_C1 cells and a decrease in T_H1/T_H2 and T_C1/T_C2 ratios.⁵ Furthermore, UVA1 irradiation induced death of SLE peripheral

blood mononuclear cells, and decreased immunoglobulin production in a dose-dependent manner.⁶

Preliminary data demonstrate safety and efficacy of low-dose UVA1 (6-20 J/cm²) in SLE.⁷⁻⁹ Several open label and three randomized, controlled, crossover trials from two research groups report benefit from UVA1 in SLE patients based on various systemic disease activity measures at doses ranging from 6-12 J/cm² for 3-9 weeks.⁷⁻¹⁰ However, the cutaneous changes in response to UVA1 treatment were not an outcome measure and were not carefully assessed. The recent validation of the Cutaneous Lupus Activity and Severity Index (CLASI) allows for a prospective trial to determine the efficacy of UVA1 in cutaneous lupus. The CLASI is based largely on physician examination of skin lesions and consists of an activity score and a damage score. It is also weighted based on the most frequently involved body surface areas to better reflect disease activity.

In these trials, no serious adverse events occurred. Polderman reported that two patients developed mild transient photosensitivity reactions with irradiation of 12 J/cm².⁹ In both patients, dose reductions to 6 J/cm² allowed continuation of therapy. Adverse events for other diseases have been minimal. With UVA1 doses several fold greater than those used for SLE (typically used for scleroderma and atopic dermatitis), the most common problems have included transient erythema, recurrence of herpes simplex virus reactivation, and polymorphic light eruptions.¹² Although difficult to assess at this time, UVA1 has not shown any clear link with skin cancer.¹³ Extensive experience with all types of UV therapy, including UVA1, indicates that phototherapy is significantly less toxic than treatment with immunosuppressive drugs. In fact, UVA1 irradiation is not absorbed by DNA (as compared with UVB which directly damages DNA bases). In a trial assessing photosensitivity in subacute cutaneous lupus erythematosus patients, no induction of lesions was seen in response to repeated doses of 20 J/cm² of UVA radiation, and the skin of one patient cleared.¹⁴

In sum, all three published randomized, controlled trials indicate that UVA1 is potentially safe and efficacious for SLE. The short duration of treatment and follow-up in these studies further limits their applicability to cutaneous lupus, a disease typically characterized by a relapsing and chronic nature. Moreover, none of these studies used the most accepted tool for measuring cutaneous lupus burden, the CLASI. Furthermore, most CLE patients are frequently seen in a dermatology setting where phototherapy may be available, making UVA1 a potentially practical therapy. Whether UVA1 is tolerated and efficacious in CLE remains an important unanswered question.

3. CONCISE SUMMARY OF PROJECT

This is an open-label trial to assess the efficacy, safety, and immunologic effects of UVA1 phototherapy on patients with cutaneous lupus erythematosus. Fifteen patients will be recruited to receive low dose (20 J/cm²) UVA1 phototherapy treatment three times per week for 10 weeks followed by an eight-week observation phase. In the event that a patient experiences adverse events (e.g. erythema) with the 20 J/cm² dose, the dose will be decreased to 6 J/cm². If symptoms persist, the patient will be withdrawn from the study. Patients will be allowed to continue on their current medications throughout the study. Patients will be assessed prior to, during, and at the end of UVA1 treatment; and at the end of the observation period. Any adverse events and symptoms of SLE flares will be assessed simultaneously. Serological studies will be completed prior to treatment, during the treatment phase, and at the end of the observation phase. Optional skin

biopsies will be performed at the beginning and end of the active treatment phase. Gene expression studies will be conducted on blood and skin samples with the intent of understanding the mechanism of action for UVA1 treatment in cutaneous lupus.

4. ELIGIBILITY CRITERIA

Criteria for Inclusion of Participants

1. Age > 18 years at enrollment.
2. Diagnosis of cutaneous lupus confirmed by clinicopathological correlation.
3. CLASI activity score of ≥ 2 .
4. Stable dose of antimalarials (hydroxychloroquine, quinacrine, or chloroquine) for 60 days.
5. Stable dose of immunosuppressive medications (e.g. mycophenolate mofetil, methotrexate, low dose prednisone <10 mg daily) for at least 30 days.
6. Stable use of topical medications including steroids (e.g. triamcinolone, clobetasol) and steroid-sparing agents (e.g. tacrolimus) for at least 30 days.
7. Patient must be able to speak and read English or Spanish at a 6th grade reading level. A translator will be available with additional consent forms in Spanish.
8. All races, ethnic backgrounds, and genders will be eligible.
9. Ability to give informed consent: Patients must be able to give informed consent or they will give assent with guardian consent.

Criteria for Exclusion of Participants:

1. Current rash consistent with acute cutaneous lupus (butterfly rash).
2. Contraindication to UVA1 phototherapy, including personal history of melanoma or non-melanoma skin cancer, history of other photosensitive disorders (e.g. porphyria cutanea tarda, polymorphous light eruption, xeroderma pigmentosum, etc.), or history of any type of organ transplant (solid organ or bone marrow).
3. Current use of frequently photosensitizing medication (e.g. tetracycline, doxycycline, isotretinoin).
4. Current or <2 months prior use of UVA1 phototherapy prior to enrollment.
5. Inability to receive UVA1 treatment safely and effectively (e.g. claustrophobia, wheelchair-bound, difficulty understanding instructions).
6. Nursing mothers, pregnant women, and women planning to become pregnant while on study are to be excluded.
7. Participants with a disease history deemed consistent with drug-induced lupus by study investigators.

5. STUDY PROCEDURES (See Appendix for Table of Study Visits)

Treatments will be delivered using Daavlin 4 Series Phototherapy Unit (Daavlin Company, Bryan, Ohio). The unit uses Philips color / 10 phosphor lamps (Phillips International, Eindhoven, The Netherlands) and an acrylic UVB-blocking filter. Photons are emitted at wavelength 340-400 nm. Participants will receive UVA1 treatment three times per week for a total of 10 weeks. An initial test dose of 6 J/cm² will be administered, followed by a test dose at 12 J/cm². Treatments will thereafter be 20 J/cm² for the remainder of the 10-week period. All participants will be required to wear UV protective, opaque goggles. Men will be required to shield their genitalia using an athletic supporter. Additionally, one or more active lesions will be covered during treatment. Treatments will be carried out during the fall and winter months.

An erythema/overdose protocol will be incorporated as follows:

Prevention: Participants will be counseled to avoid further exposure to ultraviolet light. Use of SPF 30 or higher broad spectrum sunscreen, sun avoidance, and sun protection will be required.

Treatment: Participants will be instructed to report all erythema to the study coordinator immediately. Prior to each treatment, trained nurses will interview patients for symptoms of lupus flare. The patients will be assessed by a dermatologist to determine if sunburn erythema or acute cutaneous lupus/LE-related photosensitivity is present. All such episodes will be recorded as adverse events. Patients deemed to have a lupus flare, defined as having a Systemic Lupus Erythematosus Disease Activity Index with modifications from the Safety of Estrogens in Lupus Erythematosus National Assessment (SELENA SLEDAI) score increase of >3, will be withdrawn from the study. Patients deemed to have adverse events related to UVA1 radiation (e.g. erythema) will have a dose reduction to 6 J/cm² for the duration of the study. If these symptoms recur or persist with this dose reduction, the patient will be withdrawn. Phototherapy sessions missed for non-adverse event-related reasons will be rescheduled at the earliest available date.

In order to accomplish the study aims, several variables will be measured. Participants will receive an interview, complete questionnaires, undergo a dermatologic exam, have photographic documentation, and provide blood samples at all of the study visits (see attached schedule). Skin biopsies will be optional. The outcome measures also require repeat administration of the SELENA-SLEDAI and the CLASI. Each test requires 5-10 minutes for administration.

Study Visit 1 – Initial Enrollment (Week 1, Before UVA1 Phototherapy):

The patients will have:

- Informed consent
- Full medical/family history and physical examination
- Cutaneous Lupus Erythematosus Disease Area and Severity Index (CLASI) - a measure of cutaneous lupus disease activity
- Systemic Lupus Erythematosus Disease Activity Index with modification from the Safety of Estrogens in Lupus Erythematosus National Assessment (SELENA-SLEDAI) - a measure of systemic lupus disease activity.

- **Sub-Study Procedure:** Optional 4 mm punch biopsies (three; affected-treated, affected-untreated, and unaffected skin) – Patients will have a 4 mm punch biopsy of the active (erythematosus) border of up to two lesions and site-matched (to the affected-treated site) unaffected skin (excluding lesions on the face due to cosmetic concerns). The biopsy will be performed using standard sterile technique. Skin will be closed with a single 3-0 or 4-0 polypropylene or nylon suture. Skin biopsies will be used for DNA/RNA extraction and protein expression studies.
- Clinical photography of involved areas with labeling of ≥ 1 active cutaneous lesion(s) to be covered during phototherapy, referred to as the “shielded cutaneous lupus lesion.”
- 40 cc of blood draws - Blood will be collected from a vein in the subject’s arm for autoantibody titers, complete blood count with differential, BUN and creatinine, DNA/RNA extraction and protein expression studies. The collection will take place during a scheduled research-only clinic visit by a support staff person or an investigator who has been formally trained to conduct venipuncture.
- Skindex-29+3 (modified to include cutaneous lupus-specific questions) – A quality of life survey
- Physician assessments – Study investigators will give a score from 1-10 on overall, activity, and damage aspects of each patient’s skin disease, as well as general health.
- Phototherapy orientation – The phototherapist will orient all patients to the safety protocols of the unit. Subjects will wear standard UV protective goggles and shield their genitals. A symptom questionnaire assessing symptoms of lupus flare, photosensitivity, and changes in medications will be provided at the initial phototherapy orientation. Participants will be asked to review this at home prior to each UVA1 treatment session. This questionnaire will also be reviewed at each UVA1 treatment session by the phototherapy nursing staff.
- Delivery of UVA1 phototherapy – Patients will receive UVA1 phototherapy according to the protocol stated in Table 1. **The time required to complete UVA1 treatment will be <30 minutes.**

Table 1. UVA1 Phototherapy Standard Protocol
1. Explain treatment to patient.
2. Patients should be treated three times per week.
3. Prior to each treatment session, review lupus flare and photosensitivity questionnaire.
4. Treat whole body except for genitals and “shielded cutaneous lupus lesion.”
5. Goggles should be worn at all times by the patient and the phototherapist.
6. Unit should be a fixed distance from patient. 
 • Whole body – 8-9 inches
7. Patient to apply sunscreen to nipple/areola and cover genitals.
8. Set unit to deliver appropriate dose ($\leq 20 \text{ J/cm}^2$).
9. Dose as follows: 
 a. Initial dose at 6 J/cm^2 b. Second dose at 12 J/cm^2 c. Third dose and all doses thereafter at 20 J/cm^2 in the absence of adverse effects
10. Prior to treatment, always review patient’s medications.

11. Prior to each treatment, inquire for any erythema or symptoms of lupus flare.
12. UVA1 light can induce HSV (cold sores) especially if patient has a personal history. If this occurs, notify the physician for treatment and possible prophylaxis.

Study Visit 2 –UVA1 Treatment Phase (Week 6, After 15 UVA1 Phototherapy Treatments)

The same assessment and procedures will be performed as in Study Visit 1 with the exception of informed consent, phototherapy orientation, and optional skin biopsies.

Study Visits 3 - End of UVA1 Treatment Phase (Week 11, After 30 UVA1 Phototherapy Treatments)

The same assessment and procedures will be performed as in Study Visit 1 with the exception of informed consent and phototherapy orientation.

Study Visit 4 - End of Observation Phase (Week 19, 8 Weeks After UVA1 Phototherapy Treatment Ends)

The same assessment and procedures will be performed as in Study Visit 1 with the exception of informed consent, phototherapy orientation, and optional skin biopsies.

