6. TREATMENTS

Investigational Therapy and Reference Therapy

Investigational Agent - low dose UVA1 phototherapy 3 times per week for 10 weeks

Reference therapy - none

Treatment Assignment

After obtaining informed written consent, subjects meeting criteria for inclusion will begin low dose UVA1 phototherapy in escalating doses, as described, up to 20 J/cm².

Concomitant Therapy

Patients will be allowed to continue their concomitant systemic and topical treatments, providing that they meet the inclusion criteria. However, systemic lupus flares will result in removal from the study.

Criteria for Removal from Study

- Missed treatments: If the patient misses ≥ 3 treatments, they will be removed from the study.
- Development of lupus flare, as determined by SELENA-SLEDAI score increase of at least three.
- Intolerance to UVA1 phototherapy despite dose reductions (e.g. induction of UVA1-related skin eruption such as solar urticaria or polymorphic light eruption).

In each case, the principal investigator will assess the patient and determine appropriate therapy outside the auspices of the study. These events will be recorded.

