12. SUBJECT SAFETY AND DATA MONITORING

Subject safety: Goggles will be worn at all times by the patient during UVA1 phototherapy. The patient will apply sunscreen to nipples/areolas and cover genitals. A symptom questionnaire assessing symptoms of lupus flare, photosensitivity, and changes in medications will be provided at the initial phototherapy orientation. Participants will be asked to review this at home prior to each UVA1 treatment session. This questionnaire will also be reviewed before each UVA1 treatment session by the phototherapy nursing staff. Patients will be assessed for erythema by phototherapy nursing staff prior to UVA1 treatment. Any observed erythema will be reported to the PI. Furthermore, suggestion of a lupus flare on the questionnaire will trigger immediate reporting to the PI prior to any further treatment. If a flare is verified based on investigator assessment, the patient will be withdrawn from the study. A lupus flare will be defined by having an increase in the SELENA-SLEDAI score of at least three. In the event of photosensitivity reported on the questionnaire, the PI will be notified and will evaluate the patient. If a reported reaction is deemed to be sunburn-type erythema, the dose of UVA1 will be decreased to 6 J/cm² and held at that dose throughout treatment. If symptoms persist, the patient will be withdrawn from the study. The patient's medications will always be reviewed prior to initiation of UVA1 phototherapy, but no dose change will be instituted for photosensitizing medications, given the low dose of UVA1 in this study. UVA1 light can induce HSV (cold sores) especially if the patient has a personal history. If this occurs, the PI will be notified for treatment and possible prophylaxis.

Local anesthetic is used before a skin biopsy procedure. In both the blood draw and the biopsy, guidelines are used for a sterilized procedure. All personnel performing biopsies and phlebotomy are fully trained with experience.

In the event of a patient experiencing stress from participating in this type of research, referrals for the proper counseling will be available.

Data Monitoring: All identifiable information will be kept in separate data logs and data tables. Subject specimens and samples will be labeled with unique identifiers with no identifiable information on them. Data will not be shared with investigators outside the ones listed on this project summary, yet, if shared, this data will be de-identified.

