20. APPENDIX

Procedures	Screening	Week 1	Week 6	Week 11	Week 19
Chart review	X	X	X	X	X
Medical history	X	X			
Informed consent		X			
Demographics	X	X			
Inclusion / Exclusion criteria review	X	X			
Disease history	X	X	X	X	X
Medication history and review	X	X	X	X	X
Review of systems	X	X	X	X	X
Past medical history	X	X			
Family history		X			
Smoking history		X			
Photosensitivity history and risk factors	X				
SELENA-SLEDAI administration		X	X	X	X
CLASI administration	X	X	X	X	X
Skindex-29 administration		X	X	X	X
Fitzpatrick phototyping	X	X			
Clinical assessment (with physical exam)	X	X	X	X	X
Photographs		X	X	X	X
Blood draws		X	X	X	X
Pregnancy test	X				
Optional biopsies		X		X

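### Section 5 withdraws a patient for a SELENA-SLEDAI rise of more than 3, but sections 6 and 12 do so at a rise of 3 or more, so the rules disagree at exactly +3

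*Combined protocol and SAP*

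**What the plan says.** Three places in the protocol state when a lupus flare takes a patient out of the study.

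- **Section 5, Study Procedures (erythema/overdose protocol).** A flare is defined by a SELENA-SLEDAI "score increase of >3, will be withdrawn from the study".
- **Section 6, Treatments (Criteria for Removal from Study).** The listed criterion is "Development of lupus flare, as determined by SELENA-SLEDAI score increase of at least three".
- **Section 12, Subject Safety and Data Monitoring.** "A lupus flare will be defined by having an increase in the SELENA-SLEDAI score of at least three". The consequence is the same: "If a flare is verified based on investigator assessment, the patient will be withdrawn from the study".

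The timing of assessment also matters. The Appendix table schedules "SELENA-SLEDAI administration" at weeks 1, 6, 11 and 19. In section 5, Study Visit 2 is at "Week 6, After 15 UVA1 Phototherapy Treatments" and Study Visit 3 at "Week 11, After 30 UVA1 Phototherapy Treatments". Between visits, section 12 provides that "suggestion of a lupus flare on the questionnaire will trigger immediate reporting to the PI prior to any further treatment".

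**The concern.** One event, measured on one instrument and carrying one consequence, has two cut-offs. This is a safety stopping rule: section 11 lists a flare of lupus among the short-term risks of UVA1, and safety is the first secondary aim. Section 12 makes the principal investigator solely responsible for data and safety monitoring, and no independent monitor is described who would settle an ambiguous case. The written rule therefore has to be clear.

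Two things are at stake for a patient whose score rises by exactly 3:

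- whether UVA1 has to stop, if treatment is still in progress;
- whether the rise is recorded as a flare in the safety results, at any visit after baseline.

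**Working it through.** **The three rules side by side.** Let x be the increase in SELENA-SLEDAI.

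| x | Section 5 (x > 3) | Section 6 (x ≥ 3) | Section 12 (x ≥ 3) |
|---|---|---|---|
| 0, 1, 2 | no flare | no flare | no flare |
| 3 | **no flare** | **flare, remove** | **flare, withdraw** |
| 4 or more | flare, withdraw | flare, remove | flare, withdraw |

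The rules part only at x = 3. This holds whether or not scores are whole numbers, because x > 3 and x ≥ 3 differ at that one value alone. No section ranks the definitions or assigns them to different phases or purposes.

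**When the conflict can change exposure.** Week 1 is baseline. Week 11 follows all 30 treatments, and week 19 closes the observation phase. UVA1 exposure can therefore be affected only at week 6 or at a symptom-triggered assessment during treatment. At weeks 11 and 19 the conflict cannot change exposure, but it still affects whether a flare is recorded.

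**Exposure at stake at week 6.** Inputs from section 5: first dose 6 J/cm², second dose 12 J/cm², 20 J/cm² from the third dose on, 30 sessions in all, 15 of them before the week 6 visit, and a reduced dose of 6 J/cm² after a UVA1-related adverse event.

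- Full course: 6 + 12 + 28 × 20 = 578 J/cm²
- Sessions 1 to 15: 6 + 12 + 13 × 20 = 278 J/cm²
- Sessions 16 to 30: 15 × 20 = 300 J/cm²
- Share still to come: 300 / 578 = 51.9%
- Sessions 16 to 30 on the reduced dose: 15 × 6 = 90 J/cm²

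A symptom-triggered +3 before week 6 puts more sessions at stake, and one after week 6 puts fewer.

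**Effect on the flare proportion.** With 15 patients recruited, reclassifying one moves the proportion by 1/15 = 6.7 percentage points.

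**Sample size.** The plan gives no figure for flare frequency, so there is none to reproduce. The figures in section 18 do reproduce: a one-sided one-sample t-test with n = 12, difference 20%, SD 25% and alpha 0.05 has power 0.829 by the noncentral t distribution (stated: 83%), and 12 / (1 − 0.20) = 15. Neither calculation uses the flare threshold.

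**The case against.** The strongest counter-argument is that the rules can be applied together. Section 5 says who is withdrawn above 3; it does not order treatment to continue at 3. Staff who read the whole protocol would remove the patient under section 6 and breach nothing in section 5. This is fair as far as it goes: section 6 does already require removal at +3. But section 5 gives a definition of flare, not one trigger among several, and by that definition a patient at +3 has not flared. It is also the text that describes how symptoms are handled before each treatment, so staff working from it could keep treating a patient whom section 6 removes. The flare count stays ambiguous in any case.

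A second argument is that the sign in section 5 was meant as ≥ and lost its lower bar in typing or in conversion of the PDF. This cannot be excluded. An underlined > could lose its underline while true ≥ characters survive. Nothing in the text shows that this happened, however, and ≥ appears intact in sections 4, 5 and 6, including the missed-treatments criterion just above the section 6 flare rule. If it was a lost symbol, the intended value is the one proposed below.

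A third argument is that the consequence is small. Symptoms are reviewed before every session, a single investigator makes the decisions, and the 52% describes one hypothetical patient at exactly +3 at week 6 who is kept on treatment under section 5. These limits stand. They bear on how often the conflict will matter, and they do not settle what to do when it arises.

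**Conclusion.** The inconsistency is real and lies in the current protocol text. At a SELENA-SLEDAI increase of exactly 3, section 5 does not call a flare, while sections 6 and 12 do and require withdrawal. It is a drafting inconsistency in a safety rule; the choice of three as the threshold is not in question.

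The worst case at a scheduled visit, for one patient at week 6, is 15 further sessions: 300 J/cm² at full dose or 90 J/cm² at the reduced dose. This assumes that all sessions were given as planned up to that visit. The number of patients affected cannot be worked out from the documents and could be zero. The stated power and the planned recruitment of 15 do not depend on the threshold. The case for correcting it rests on the nature of the rule, mandatory withdrawal for a recognised harm of the treatment, and not on expected frequency.

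**What to change.** In section 5, replace the strict threshold with an increase of at least three (≥3), so that sections 5, 6 and 12 state one rule. Two of the three sections, including the formal removal criteria, already use this value, and it is the more protective one. Use the same definition when flares are counted and reported for the safety aim.

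The cost is one wording change by amendment, with no added visit, procedure or patient. The only downside is that a patient at exactly +3 is always withdrawn, which sections 6 and 12 already require.

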7. SOURCES OF RESEARCH MATERIAL

Skin Biopsy

4 mm punch biopsies (three; affected-treated, affected-untreated, and unaffected skin) of up to 15 patients will be performed under local anesthesia by an investigator who has been formally trained to perform a skin biopsy. The biopsies will be performed using standard sterile technique. Skin will be closed with a single 3-0 or 4-0 polypropylene or nylon suture. These biopsies will take place during Study Visits 1 and 3 during a scheduled research-only clinic visit. The investigator will avoid cosmetically sensitive areas such as the face for biopsies, unless the patient permits.

Blood

Approximately 40 cc of blood will be collected from a vein in the subject's arm at the Study Visits during a scheduled research-only clinic visit by a support staff person or an investigator who has been formally trained to conduct venipuncture.

Patient Data

Other data used in the research will be obtained from the subjects' medical records and in-person interviews. The data sought will include the subject's age, gender, race, age of diagnosis, contact information, disease location, presentation and history, associated symptoms, past and current treatments, personal history of autoimmune diseases, family history, and quality of life assessments. At return study visits, subjects will update the investigators on changes to their disease history, associated symptoms, treatments, quality-of-life assessments, and will be assessed for adverse events. At each Study Visit, an investigator will perform a skin examination, obtain severity index scores for cutaneous and systemic lupus (i.e. CLASI, SELENA-SLEDAI), provide physician's assessment of disease activity, and obtain photographs.

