8. LABORATORY PROCEDURES

Differences in gene expression before and after UVA1 treatment may yield insight into possible mechanisms of action for UVA1 treatment in cutaneous lupus. To investigate expression of individual genes, DNA and RNA testing will be conducted on both blood and skin samples. Planned experiments include microarray analyses to generate global expression patterns of multiple genes and RT-PCR for verification of gene expression. Skin biopsy and blood samples may also be used for assessment of protein expression using immunohistochemistry and flow cytometry, respectively.

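### The Week 11 skin biopsy inherits the Visit 1 rule of sampling an active border, so which tissue is taken depends on treatment response and the skin change in Aim 3 may be understated.

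*Combined protocol and SAP*

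**What the plan says.** Section 5, Study Visit 1, Sub-Study Procedure, gives the rule for lesional tissue: "Patients will have a 4 mm punch biopsy of the active (erythematosus) border of up to two lesions". Unaffected skin is to be site-matched to the treated lesion.

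Study Visit 3 (Week 11, after 30 treatments) is defined by cross-reference: "The same assessment and procedures will be performed as in Study Visit 1 with the exception of informed consent and phototherapy orientation". The parallel sentences for Visits 2 and 4 also except the biopsies; the one for Visit 3 does not. Section 7 agrees: "These biopsies will take place during Study Visits 1 and 3". So does the Appendix table, which marks optional biopsies at Weeks 1 and 11.

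Section 7 lists the specimens as "4 mm punch biopsies (three; affected-treated, affected-untreated, and unaffected skin) of up to 15 patients". At Visit 1 the photography step calls for "labeling of ≥ 1 active cutaneous lesion(s) to be covered during phototherapy". No equivalent marking is described for the treated lesion that is biopsied.

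The specimens serve Aim 3 in Section 1, which expects UVA1 to "decrease T cells, B cells, and plasmacytoid dendritic cells in skin". They also serve Section 8: "Differences in gene expression before and after UVA1 treatment may yield insight into possible mechanisms of action".

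No section says that the Visit 3 specimen comes from the lesion biopsied at Visit 1, where it should lie relative to the earlier punch, or what to do if no active border remains.

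**The concern.** At Visit 1 an active border is a sensible target, because nothing has yet been treated. At Visit 3 the same words make sampling conditional on a post-treatment outcome. The primary hypothesis is that "CLE patients treated with low dose UVA1 phototherapy will experience clinical improvement". If that is right, some treated lesions will have lost their active border by Week 11. A fully cleared lesion then gives no sample, or another lesion that is still active is taken in its place. A partly cleared lesion is sampled at the part that has not responded.

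In each case responding tissue is under-represented at the second time point. If immune cells and gene expression change most where the lesion improves, the estimated decrease moves towards zero. If UVA1 works, shielded lesions should keep an active border more often than treated ones, so the selection falls unequally on the two specimen types and also weakens the contrast between them. Analysis cannot repair this afterwards, because the tissue that would have shown the change was never taken.

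**Working it through.** **The plan's own figure.** Section 18 gives the only sample-size statement: n = 12, difference 20%, SD 25%, one-sided one-sample t-test at 0.05, power 83%. The noncentrality is (20/25) × √12 = 2.77 on 11 degrees of freedom, and the power is 0.829, so the figure reproduces. Recruitment also checks: 12/(1 − 0.20) = 15. Neither figure concerns the biopsies, for which no sample size is given.

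**Inputs for the bias.** The documents give no clearance rate, marker variance or expected marker change, so these are assumptions:
- c, the share of biopsied treated lesions that have cleared by Week 11: 10% to 75%.
- r, the marker change in still-active lesions as a fraction of the change in cleared ones: 0.25 or 0.5.

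**Formula.** Set the change in cleared lesions to 1. Sampling the same lesions whatever their activity estimates c + (1 − c)r. Sampling only lesions with an active border estimates r. The share of the true change retained is r / [c + (1 − c)r].

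| c | r = 0.25 | r = 0.5 |
|---|---|---|
| 10% | 0.25/0.325 = 77% | 0.5/0.55 = 91% |
| 25% | 0.25/0.4375 = 57% | 0.5/0.625 = 80% |
| 50% | 0.25/0.625 = 40% | 0.5/0.75 = 67% |
| 75% | 0.25/0.8125 = 31% | 0.5/0.875 = 57% |

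The end cases bound the result. With r = 1 (marker change unrelated to clearing) the retained share is 100% and there is no bias. With r = 0 nothing is retained.

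**Treated versus shielded.** If shielded lesions neither clear nor change, the contrast is c + (1 − c)r − 0 under same-lesion sampling and r − 0 under active-only sampling, so the retained shares are those in the table.

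**Simulation.** As a check without the two-class simplification, 400,000 patients were simulated with two lesions each, continuous lesion activity, and a marker correlated 0.3 to 0.9 with activity. Treatment effects were set so that about 20%, 41% and 60% of the biopsied lesions cleared. The retained change was 60% to 80% if cleared lesions gave no sample, and 51% to 64% if they were replaced by the patient's other lesion when that was still active.

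**Loss of pairs.** If cleared lesions give no sample, then of 12 completers who all accept biopsy, 12 × (1 − c) pairs remain: 9 at 25% clearance, 6 at 50% and 3 at 75%. Because biopsy is optional, the real numbers could be lower.

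**The case against.** The best counter-argument is that the Visit 3 cross-reference is shorthand for which activities recur and was never meant to fix lesion choice. It cannot be fully literal. Visit 1 also lists delivery of phototherapy and labelling of lesions to be covered, and neither is excepted at Visit 3 or at Visit 4, when treatment has ended. The Appendix confines family history to Week 1 and medical history to screening and Week 1, although the cross-reference excepts neither.

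The specimen names also point to fixed lesions. At Visit 1 nothing has been treated, yet specimens are already called affected-treated and affected-untreated, which makes most sense if lesions are assigned then and followed. The shielded specimen must come from a lesion labelled at Visit 1 and covered throughout, so free substitution is not available there.

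Much of this stands. A reader might infer that the protocol tells investigators to skip or replace cleared lesions; it does not say so, and a careful investigator could return to the same lesion. But if the cross-reference is only shorthand, Visit 3 has no sampling rule, and tissue is chosen after the response has been seen. If the same lesion is intended, the active-border wording still picks its unresponsive part or yields nothing. Fixed lesions narrow the problem but do not remove it.

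A reader might also fear that wound repair at the first punch site distorts the result. No section calls for re-punching the same spot, and any such effect would apply to treated and shielded lesions alike. It is a reason to state the location, not a separate finding.

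**Conclusion.** The point holds as a gap in the Visit 3 sampling rule that allows outcome-dependent tissue selection. The direction is towards no effect, provided that markers fall more where lesions clear, which fits the trial's own hypotheses. About 31% to 91% of the true change is retained over the assumed ranges (r from 0.25 to 0.5, c from 10% to 75%). The documents cannot narrow this, and the bias is nil if marker change is unrelated to clearing.

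Two stronger readings are not supported. One is that the skin result must come out near zero however many lesions clear. That needs still-active lesions to show no marker change at all (r = 0), for which the documents give no basis. The other is that the trial's efficacy conclusion is compromised. The biopsies are optional and serve only the skin part of the third secondary aim; CLASI, safety, quality of life, blood markers and the 83% power figure are untouched. The change is worth making because it is cheap and the lost tissue cannot be recovered.

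**What to change.** In Section 5, under Study Visit 1, add that the biopsied treated lesion is labelled and photographed as well as the shielded one, with the sampled border site marked. The current text labels only the lesions to be covered, so existing photographs may not identify the treated site.

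Under Study Visit 3, replace the bare cross-reference for biopsies with a specific rule:
- Sample the same treated lesion and the same shielded lesion as at Visit 1.
- Sample at the original border location, next to but outside the earlier scar, whether or not erythema remains. Keeping to the border avoids comparing border tissue at Visit 1 with central tissue at Visit 3.
- Record residual activity at the site.
- Do not substitute another lesion. If the lesion cannot be sampled, record the specimen as missing.
- Report missing Visit 3 specimens alongside clinical response.

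The cost is a little more photographic labelling and a few sentences of text, with no additional biopsies or visits. Some Visit 3 specimens will come from resolved skin, which is what Aim 3 needs. Lesions chosen while active can also improve somewhat without treatment: with no treatment effect, the simulation gave a fall of 0.008 to 0.035 marker standard deviations under same-lesion sampling. The shielded lesion, sampled by the same rule, is the guard against reading that as a UVA1 effect.
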